Analysis Plan

Official Title: Veterans Justice Reentry (Post-Incarceration) (QUE 15-284)

Brief Title: Improving Linkage to Health and Other Services for Veterans Leaving Incarceration (PIE)

ClinicalTrials.gov ID: NCT02964897

Unique Protocol ID: QUX 16-012

Study Principal Investigator: D. [name] MS BA

Document date: September 7, 2021

Analysis Plan:

Improving Linkage to Health and Other Services for Veterans Leaving Incarceration (ID QUX 16-012)

We will enroll Veterans on a rolling basis as released from MA correctional facilities. We will use HOMES database to create a historical comparison group comprised of all Veterans released in MA in the two-year period directly preceding the start of the PIE intervention and who accessed VA Health Care for Reentry Veterans (HCRV) services.

Quantitatively, we will use HOMES and CDW to compare intervention and comparison Veterans with respect to their baseline demographic characteristics (age, gender, race, ethnicity, marital status, self-rated health) and our outcomes interest. Also for intervention Veterans we will have self-report diagnoses and utilization from baseline and 6-month follow up (including utilization of non-VA health care sources). We will compare rates of visits for primary care, outpatient MH treatment, outpatient SUD treatment, as well as missed opportunities (e.g. no shows) between intervention and comparison groups using t-tests and chi-square tests. For our secondary measures we will also compare intervention to comparison on ER and hospital use (episodes and # of days) during the 6-month reentry period.

Analysis involves two phases. First, we use descriptive statistics to summarize the volume and intensity of peer activities in support of the Post-Incarceration Engagement (PIE) intervention participants. Secondly, to examine access to and engagement in care outcomes, we compare our measures of linkages to VA health care following release between PIE participants and our historical comparison group. Specifically, we use bivariate tests (Chi-Square/Fisher Exact Tests and t-tests, as appropriate) to assess the relationship between participation in the PIE intervention and linkages with VA health care.

Summary of key variables

- Demographics (age, gender, race, ethnicity, marital status, self-rated health)
- SUD diagnoses
- MH diagnoses
- Criminal offense
- Length of incarceration
- # of arrests
- Housing/homeless experience
- Major comorbidities (out of list of 10-12)
- Visits to primary care
- Visits to MH outpatient care
- Visits to SUD outpatient care
- ED encounters
- Inpatient hospitalizations
- No shows at the above appointments

All data will be stored on VINCI and all analysis will be conducted on VINCI

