The HCRV program was started to combat these issues. A designated outreach specialist works with incarcerated VHA-eligible Veterans to establish a post-release plan for linkage to VHA services (2014). This program, with 1-2 outreach specialists per state, has improved the connection between reentry Veterans and the VHA. However, our analyses of homeless program data linked to CDW indicate that 43% of eligible HCRV Veterans **do not** have a VHA outpatient contact in the first 4 months post incarceration. Reducing this number is critical given the elevated rates of chronic health conditions, as well as MH or SUDs in this population (Noonan 2007; Taxman 2010; Maruschak 2012). To address this gap, we will work with the national HCRV office to implement an evidence-based peer support intervention to extend the reach and effectiveness of the HCRV program in linking Veterans to VHA. Peers with incarceration experience are likely to better understand and connect with Veterans on a personal level than the outreach specialist, and thus are more likely to maintain contact and link to VHA during the first months post-release (Blodgett 2013; Chinman, George et al. 2014; Bagnall, South et al. 2015). Peers are gaining popularity in forensic settings (called “forensic peer specialists”) with civilian populations and would likely be beneficial for a Veteran population (Miller and Massaro 2008). The aims of this project are,

1. Conduct contextual analysis to identify VA and community reentry resources, and to describe how reentry Veterans use them.
2. Implement peer-support to link reentry veterans to VHA primary, mental health, and SUD services. We will use external and internal facilitation as the implementation strategy.
3. At the end of this project, we will develop a proposal for a multi-VISN expansion study, which will use a hybrid type III, stepped-wedge design, to demonstrate effectiveness in multiple geographic and contextual settings.

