Phase 2 - MA Implementation of Peer Support. This phase involves implementation and evaluation of the peer-support intervention in MA. For Population, Recruitment of Veterans, Inclusion/Exclusion, see Phase 1, above. Our target is 30 Veterans receiving peer support. We will enroll Veterans on a rolling basis as released from MA correctional facilities. We will use HOMES database to create a matched comparison group of Veterans released in the same time period in MA, matching on demographics, SUD/MH diagnoses, criminal offense, length of incarceration, and # of arrests. Intervention will last for 6 months for any single Veteran, with peers having caseloads of 15 Veterans (Dihoff 2009). A VISN 1 outreach specialist, [name], will serve as

internal facilitator, while [name] and [name] will be external facilitators. Peer Training: see above in “Peer-Support Intervention”.

Data Sources, Collection and Analysis: Peers will administer a health care utilization questionnaire with intervention Veterans at baseline (week 1) and at 6 months to capture information about VA and non-VA health service use (the former for comparison with VA medical record data).

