Additional Design Considerations: The focus of the *Post-Incarceration* project is to develop implementation methods, materials and training, identify appropriate level of internal facilitation, and assess dissemination processes across different states. It is not designed to demonstrate a statistically significant effect of the intervention. With the anticipated sample size of 30 in the peer-support intervention groups and the 30 in the comparison group, the linkage rate, now at 57%, would need to increase by at least 20% to detect the intervention effect with 80% power at the 0.05 significance level. However, our measurement of these outcomes in the current project will allow us to estimate effect sizes and sample sizes for the next phase of this implementation, i.e. a cluster-randomized multi-VISN hybrid implementation-effectiveness study (this next phase will occur after the current project, supported by a separate funding source).

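### The historical comparison group shares no release period with PIE and release date is never used, so any calendar drift in linkage is fully confounded with PIE and goes unchecked

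*SAP*

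**What the plan says.** The SAP takes its comparison group from HOMES: "all Veterans released in MA in the two-year period directly preceding the start of the PIE intervention", restricted to those who accessed HCRV services. PIE participants are enrolled on a rolling basis as they are released. For the linkage outcomes the SAP states "we use bivariate tests (Chi-Square/Fisher Exact Tests and t-tests, as appropriate".

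The SAP also compares the groups on "baseline demographic characteristics (age, gender, race, ethnicity, marital status, self-rated health". Its summary of key variables adds diagnoses, offence, length of incarceration, arrests, housing and comorbidities. Release date is in neither list. The protocol's Key Covariates paragraph (section 3, Phase 2) does not name it either.

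The protocol plans a different comparator. Section 3, Phase 2, describes a "matched comparison group of Veterans released in the same time period in MA", matched on personal and offence characteristics.

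On use of the result, the protocol's Additional Design Considerations say the project is not designed to show a statistically significant effect, but that its outcomes will supply effect sizes and sample sizes for the next study.

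**The concern.** A same-period comparator controls calendar time by design: whatever changes in HCRV staffing, VHA access or corrections practice affects both groups alike. The SAP's group gives up that protection and puts nothing in its place. A rise in linkage unrelated to PIE would be counted as a PIE effect, and a fall would hide one. Matching or adjusting on age, diagnoses or offence does not remove a calendar trend.

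The root of the problem is the non-concurrent group. Pooling its 24 months into one sample only keeps any drift out of sight; a date-stratified historical group would still have to be extrapolated into the PIE period. What is at stake is mainly the point estimate, because that is what goes forward to size the next study.

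**Working it through.** **The plan's own figure.** For two groups of 30, the protocol's power statement is that "the linkage rate, now at 57%, would need to increase by at least 20" per cent (80% power, 0.05 level). Reading this as 57% to 77%, two-sided, with pooled variance:

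power = Φ[(0.20 − 1.96·√(2·0.67·0.33/30)) / √((0.57·0.43 + 0.77·0.23)/30)] = Φ[(0.200 − 0.238)/0.119] = 37%.

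The increase detectable with 80% power is about 31.6 points. The stated figure therefore does not reproduce. That is a separate matter and nothing below depends on it, but it is why I scale the bias against the standard error and not against 20 points (the text also does not say whether the 20% is points or relative).

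**Inputs**
- From the documents: a 24-month historical window; 30 PIE Veterans; linkage 57% (from the protocol's 43% without a "VHA outpatient contact in the first 4 months post incarceration"), used here only for the variance; about 200 Massachusetts releases a year, so at most about 400 comparators before the HCRV restriction.
- Assumed: linear drift; releases spread evenly; 100 to 400 comparators; accrual of 3.6 to 12 months. The lower end is 30 Veterans drawn from half of the annual releases: 30/100 × 12 = 3.6. Drift of 2 or 5 points a year is a scenario only.

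**Gap and bias.** The historical releases centre 12 months before PIE starts and the PIE releases centre half the accrual period after.

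Gap = 12 + accrual/2 = 13.8 to 18 months. Bias = drift × gap/12.
- 2 points a year: 2.3 to 3.0 points.
- 5 points a year: 5.75 to 7.5 points.

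**Against sampling error.** SE = √(0.57·0.43·(1/30 + 1/n)) = 9.4 points for n = 400 and 10.3 for n = 100. Rejection rate with no true effect = Φ(−1.96 + bias/SE) + Φ(−1.96 − bias/SE):
- 5 points a year: 9.4% to 12.6% (n = 400); 8.6% to 11.3% (n = 100).
- 2 points a year: about 6%.

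**Restricting to the last 12 months.** The historical centre moves to 6 months before the start, so the gap is 6 + accrual/2 = 7.8 to 12 months. Bias at 5 points a year becomes 3.25 to 5.0 points. The cut is 6/13.8 = 43% down to 6/18 = 33%. With n halved, SE = √(0.2451·(1/30 + 2/n)), which is 3% (n = 400), 6% (n = 200) or 11% (n = 100) larger.

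**Adding a linear release-date term** (difference scale, slope taken from the historical group). The comparator variance is multiplied by f = 1 + gap²/(24²/12), which is 4.97 at 13.8 months and 7.75 at 18 months. SE = √(0.2451·(1/30 + f/n)).

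| Comparators | Interval wider, gap 13.8 months | Interval wider, gap 18 months |
|---|---|---|
| 400 | 13% | 21% |
| 200 | 23% | 37% |
| 100 | 38% | 60% |

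**Can the historical data show the drift?** The SE of the historical slope is √(0.2451/(n·2²/12)) = 4.3, 6.1 and 8.6 points a year for n = 400, 200 and 100. Power to detect 5 points a year is about 21%, 13% and 9%. Half-year rates have an SE of √(0.2451/(n/4)) = 5 to 10 points.

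**The case against.** A reader might infer that the protocol itself reports rising linkage, because section 1 says HCRV "has improved the connection between reentry Veterans and the VHA". The documents do not support that. The remark is undated, describes what the program has achieved since it began, and is followed by a single pooled linkage figure. There are no rates by year, and no trend is shown within the two-year window or between it and PIE. Nor can one infer that a PIE difference would be spurious: drift could run either way or be absent.

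The other objections are fair and mostly stand. This is a generic limitation of historical controls. At 2 points a year the bias is about a third of a standard error or less, and even at 5 it stays below one. The test's error rate matters little in a project that disclaims a significance goal. A trend table has little power, so a flat one could reassure falsely. Restricting the window leaves more than half of the bias, and the date model extrapolates a poorly estimated slope.

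These points limit the weight of the concern and the strength of the remedy. They do not answer the core of it: the groups share no release period, the plan never looks at release date, and the estimate is meant to be reused.

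**Conclusion.** The concern holds in limited form. Calendar time is fully confounded with PIE under the SAP, which follows from the definitions alone and needs no assumption about drift. How much this matters cannot be taken from the documents. In the assumed scenario of linear drift at 5 points a year, even releases and 3.6 to 12 months of accrual, the bias is about 6 to 7.5 points, with a rejection rate of roughly 9% to 13% in place of 5%. At 2 points a year it is 2.3 to 3.0 points and nearly harmless. The practical consequence is a possibly mis-sized next study. This is a worthwhile improvement of minor severity, and no analysis of the historical group alone can remove the problem.

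**What to change.** Keep the planned comparison and add the following to the SAP before the outcome data are examined:

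1. **Sensitivity analysis (a):** the same comparison using only historical Veterans released in the last 12 months of the window. It cuts linear-drift bias by about 33% to 43%, for an interval about 3% to 11% wider.
2. **Sensitivity analysis (b):** a logistic model with PIE and a linear release-date term. It removes linear drift only, for an interval about 13% to 60% wider (400 down to 100 comparators), which is why it should not be primary.
3. **Description:** historical linkage by release half-year with confidence intervals, and a sentence that a flat table is not evidence of no drift.
4. **Reporting:** the planned estimate, (a) and (b) side by side with intervals, without a pass/fail robustness rule. State residual calendar-time confounding as a limitation, and repeat it wherever the effect size is carried into the next study's sample size.
5. **Reconciliation:** align the SAP's historical group with the protocol's same-period matched group. Say which is intended and, if the historical one, why.

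The cost is SAP and protocol wording, one table and two short analyses. No new data collection should be needed, since HOMES must hold release dates for the two-year window to be applied at all.

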Phase 1: Contextual Analysis and Preparation for Implementation in Massachusetts. We will conduct contextual analysis (Chambers, Mustard et al. 2013; Chambers, Glasgow et al. 2013; Lyon, Pullmann et al. 2015) through interviews and network mapping (Aim 1). At the end of this phase the findings will be incorporated into the peer-support guidebook. This phase will involve interviewing Veterans (thrice over 6 months) and stakeholders (once). Network mapping is a technique used in business and engineering, and is increasingly being applied in health care. It involves documenting potential paths that individuals and groups follow in the process of accomplishing a task (here, linkage to primary care and other health services)(Lyalin and Williams 2005; Williams, Lyalin et al. 2005; Rico, Yalcin et al. 2014). We use interview questions that seek temporal, spatial, and participatory information. The timing, sequence, and duration of Veterans' contacts with individuals and organizations are mapped in an activity diagram (Lyalin and Williams 2005), which are then combined to comprehensively map the network of reentry-related contacts that Veterans make. These maps may reveal unhelpful contacts, waiting between contacts, and useful but infrequently tapped resources. Population: There are about 200 Veterans, released from Massachusetts prisons each year. Recruitment of Veterans: We will use a method currently in use VHA by a contractor, Policy Research Associates (Delmar, NY), to contact reentry Veterans. During prison visits, the outreach specialists will collect contact information from incarcerated Veterans who indicate willingness to participate in the project after their release. The outreach specialist will provide our team with the contact sheets of those Veterans and their release dates. We will contact these Veterans after their release, enrolling 10 Veterans. Inclusion/Exclusion: Released from an MA state prison, eligible for VHA services, and no history of dementia.

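### PIE Veterans are selected on willingness, post-release contact and stated eligibility; the SAP's historical comparators are not, so the bivariate comparison is open to selection bias of unestablished size and direction

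*SAP*

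**What the plan says.** **Intervention side.** Protocol Section 3, Phase 1, describes recruitment in two steps. "During prison visits, the outreach specialists will collect contact information" from "incarcerated Veterans who indicate willingness to participate in the project after their release". The team then acts on those sheets: "We will contact these Veterans after their release". The eligibility line reads "Released from an MA state prison, eligible for VHA services, and no history of dementia". Phase 2, the intervention phase, takes all of this over: "For Population, Recruitment of Veterans, Inclusion/Exclusion, see Phase 1, above".

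**Comparison side.** The SAP replaces the protocol's matched concurrent group with a historical one: all Veterans released in MA in the two years before PIE started "and who accessed VA Health Care for Reentry Veterans (HCRV) services". It states no willingness, contact, facility-type or dementia condition, and does not say what counts as accessing HCRV.

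**Analysis.** For linkage, "we use bivariate tests (Chi-Square/Fisher Exact Tests and t-tests, as appropriate". The SAP compares baseline demographics but states no matching, weighting or adjustment. The protocol's Key Covariates paragraph names any past VHA use and time since last VHA use as possible explanations of outcome differences; the SAP's list of key variables has neither.

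**Use.** The protocol's Additional Design Considerations say that the project is not built to show a significant effect, but that its outcomes will supply effect sizes and sample sizes for the next study. Section 4 says that the project will help answer whether peer support raises linkage.

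**The concern.** Willingness to join and being reachable after release may both go with linking to VHA. Section 2 of the protocol cites a study of Veterans leaving Los Angeles jails in which reluctance to link was common, so attitude is a plausible correlate of the main outcome. Section 1 reports that 43% of eligible HCRV Veterans have no VHA outpatient contact in the first four months, so linkage varies a good deal within the HCRV population. Selecting further inside that population can therefore shift the rate.

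If it does, the difference between PIE and historical Veterans mixes peer support with who was selected. A confidence interval does not cover this, and more comparators do not reduce it. What is at stake is the effect size passed to the next study and the answer given to the linkage question.

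**Working it through.** **1. Conditions side by side**

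| Condition | PIE (protocol, Phase 1 via Phase 2) | Historical group (SAP) |
|---|---|---|
| Willingness stated in prison | Required | Not stated |
| Contacted by the team after release | Required | Not stated |
| HCRV | Recruited through outreach specialists' prison visits | Accessed HCRV, undefined |
| Facility | MA state prison | Any release in MA |
| VHA-eligible | Required | Not stated; probably shared, since Section 1 says HCRV works with eligible Veterans |
| No dementia history | Required | Not stated |

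HCRV involvement is a partly shared filter. On facility type, Section 2 says that HCRV covers state and Federal prisons and that its identification and planning work takes place in prisons and jails. The historical group can therefore include releases that the Phase 1 criterion excludes. There is one uncertainty on the PIE side. Phase 2 and the SAP describe enrollment more broadly ("We will enroll Veterans on a rolling basis as released from MA correctional facilities"), so which facility criterion was applied needs confirming.

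Willingness and contactability are not among the protocol's matching variables, its covariates or the SAP's variables.

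**2. Size: illustration only**

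The plan gives no figure for this selection, so there is none to reproduce. The base rate is the protocol's 57% (100% - 43%). That is a four-month HCRV figure, and its use for MA over six months is an assumption. Let f be the share of comparators who would have been willing and reached, and RR their linkage rate divided by that of the rest. Both are assumed. With no peer-support effect,

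p_sel = RR × 0.57 / (f × RR + 1 - f), and bias = p_sel - 0.57.

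Example, f = 0.5 and RR = 1.5: 0.855 / 1.25 = 0.684, so +11.4 points. Example, f = 0.5 and RR = 0.8: 0.456 / 0.90 = 0.507, so -6.3 points.

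| f | RR 0.8 | RR 1 | RR 1.25 | RR 1.5 |
|---|---|---|---|---|
| 0.5 | -6.3 | 0 | +6.3 | +11.4 |
| 0.8 | -2.7 | 0 | +2.4 | +4.1 |
| 0.9 | -1.4 | 0 | +1.2 | +2.0 |

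Smaller shares widen the range. At f = 0.3 it is -8.5 to +17.3 (0.456/0.94 and 0.855/1.15, each less 0.57). At f = 0.15 it is -10.0 to +22.5 (0.456/0.97 and 0.855/1.075).

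**3. Precision and the cost of restricting comparators**

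The 95% half-width with 30 PIE Veterans and n comparators is 1.96 × √[0.57 × 0.43 × (1/30 + 1/n)].

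- n = 400: 18.4 points. This is about 200 MA releases a year (protocol, Phase 1) over two years, an upper figure before the HCRV restriction.
- n = 200: 19.0 points.
- n = 100: 20.2 points.

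The 30 PIE Veterans dominate the error, so filtering the historical group costs little.

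**4. A comparison not selected on contact**

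If N Veterans are analysed on the PIE side and only 30 received PIE, a 20-point effect shows as 20 × 30/N. The half-width against 400 is 1.96 × √[0.57 × 0.43 × (1/N + 1/400)].

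| N (assumed) | Effect shown | Half-width |
|---|---|---|
| 40 (contact sheets) | 15.0 | 16.1 |
| 60 (contact sheets) | 10.0 | 13.4 |
| 100 (all HCRV releases during enrollment) | 6.0 | 10.8 |
| 200 (all HCRV releases during enrollment) | 3.0 | 8.4 |

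In every row the half-width exceeds the effect shown, so this is at best a rough check.

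**The case against.** Any comparison of consenting participants with a records-based control differs in willingness. The protocol disclaims a significance aim and allows that other factors may partly explain differences, and the SAP speaks only of a relationship between participation and linkage. HCRV involvement is partly shared. The illustrated bias rests wholly on assumed inputs, and at shares of 80-90% it is at most about 4 points against random error of 18.4. Filtering on eligibility, facility and dementia does not touch willingness or contact. The prior-VHA-use variables are at best proxies, and nothing in the SAP expressly withdraws the protocol's plan to examine them.

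Much of this stands: the size is unknown, and the filters do not remove the central selection. It does not remove the point. The protocol still sends the estimate to the next study and to the linkage question, and the SAP neither discloses this selection nor adjusts for anything. The filters deal with a separate, correctable mismatch in who can enter each group.

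A reader might infer that the bias favours PIE. That is plausible for linkage and visits, but the documents give no data on it. If accessing HCRV means access after release, the comparators are also selected on engagement. For no-shows, ER and hospital use the direction is unclear.

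**Conclusion.** The concern holds as a design weakness that should be fixed. The entry conditions differ in the text, the outcome tests are bivariate, and the two most relevant recordable variables are missing from the SAP's list. Confidence is medium, because the intervention side rests on the protocol (the SAP does not restate recruitment) and access to HCRV is undefined.

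Neither size nor direction is established. The range of -6.3 to +11.4 points depends on the assumed 50-90% share, the assumed ratios of 0.8 to 1.5 and the 57% base; other assumptions give wider ranges. A reader might infer that selection could account for a whole 20-point gain. Some assumed inputs produce that, but nothing in the documents shows that they apply. Nor do the documents show that the historical group does contain jail or Federal releases, only that its definition allows them.

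**What to change.** 1. **Align the groups.** In the SAP, use HOMES/CDW to restrict the historical group to the recordable criteria applied to PIE: VHA-eligible, no dementia diagnosis, and the same facility type, after confirming whether the state-prison criterion or the broader correctional-facilities wording was used. State what counts as accessing HCRV and when.
2. **Use the protocol's covariates.** Carry past VHA use and time since last use into the SAP. Report linkage adjusted for or stratified by them, next to the bivariate test.
3. **Limit the claim.** State that selection on willingness and contact, and change over calendar time, remain. The difference is not to be read as the peer-support effect, nor passed to the next sample size without allowance for this. Report the numbers willing, contacted and enrolled.
4. **Optional.** If CDW access to non-enrolled Veterans is permitted (an assumption), compare all contact-sheet Veterans, or all HCRV Veterans released in MA during enrollment, with the historical group. Label it a rough check that does not address calendar time.

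**Cost.** Database filters, two baseline variables, a recruitment-flow table and a limitation statement. Contact sheets and release dates already go to the team. The comparator pool shrinks, but the half-width grows only from 18.4 to 20.2 points if it falls from 400 to 100. Room for covariates is limited: at 57% linkage, 30 PIE Veterans give about 17 linked (30 × 0.57) and 13 not, so the adjusted model should stay small.

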2. RATIONALE

Reentry from incarceration is a precarious time. Individuals (including Veterans) leaving incarceration often have complicated biopsychosocial needs (Mallik-Kane 2008). They face many barriers to accessing needed services for co-occurring substance use and MH disorders, infectious diseases, other chronic medical conditions. Homelessness, unemployment, and financial instability are prevalent ([name] 2003; Travis 2005; Baillargeon, Giordano et al. 2009; Meyer, Chen et al. 2011; [name] 2015). Literally overnight they experience sudden responsibilities, and competing needs, and yet they have rusty social and self-management skills, and may mistrust service providers and health care systems ([name] 2003; Meyer, Chen et al. 2011; Anaya 2012).

A 2012 study examined Veterans leaving Los Angeles jails and found that, commonly, Veterans held negative views of the VA and were resistant to link to VHA services upon their release (Anaya 2012). Peers may help bridge this mistrust.

Reentry represents a major break in continuity of care (Palepu 2004; Springer and Altice 2005; Harzke 2006; Baillargeon, Giordano et al. 2009; Massoglia 2009; Meyer, Chen et al. 2011). Compared to the other pressing needs, health needs are often de-prioritized by the reentering individual due to drug use relapse and/or untreated mental health disorders (Seaman 1198; [name] 2003; Inciardi 2007; Pettus-Davis 2009; Rebholz 2009; Merrall 2010; Meyer, Chen et al. 2011; [name] 2015). Without addressing a Veteran's behavioral and physical health issues, the other components of reentry and reintegration (housing, employment, family, etc.) can be undermined, which may lead to unstable housing or homelessness, or repeat incarceration. The VA established the HCRV program to: 1) identify Veterans incarcerated in state and Federal prisons, 2) conduct a clinical assessment of these Veterans' needs, and 3) link them to the services that they need when they transition back to the community after they complete their sentence (2014; 2015; 2015).

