Analysis: During implementation we will collect formative evaluation data about the intervention through interviews (5 stakeholders and 5 Veterans). We will assess elements of the implementation by learning what meanings the participants (stakeholder, peers, Veterans) assign to the intervention and the processes that the intervention is designed to affect (Orlikowski and Baroudi 1991). We will also conduct summative evaluation, including qualitative interviews (5 Veterans and 5 stakeholders) to evaluate, for example, whether peers were *Enabling* linkage to and engagement in health care, and whether this helped address Veteran’s health care *Need*. With stakeholders we will explore the effectiveness of external and internal facilitation, and identify facilitators and barriers to implementation. Quantitatively, we will use HOMES and CDW to compare intervention and comparison Veterans. Also for intervention Veterans we will have self-report diagnoses and utilization from baseline and 6-month follow up (including utilization of non-VA health care sources). We will compare rates of visits for primary care, MH, and SUD between intervention and comparison groups using t-tests and chi-square tests. For our secondary measures we will compare intervention to comparison Veterans on ER and hospital use (episodes and # of days) during the 6 month reentry period.

Key Covariates. We will use CDW and HOMES data to evaluate whether there are substantial differences between the intervention and comparison Veterans at baseline. This approach accounts for the possibility that observed differences in our outcomes, such as linkage rates, may be partially explained by factors such as duration of sentence, severity of crime, number of incarcerations, ever used VHA services, length of time since last used VHA services, and socio-demographics such as age and race.

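### The SAP leaves out prior VHA use, which the protocol names as a possible explanation for linkage differences, so an imbalance between PIE volunteers and the historical group would go unseen

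*SAP*

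**What the plan says.** **Protocol, section 3, Key Covariates.** The plan is stated as "We will use CDW and HOMES data to evaluate whether there are substantial differences between the intervention and comparison Veterans at baseline". The reason given is that "observed differences in our outcomes, such as linkage rates, may be partially explained by factors such as duration of sentence" and others. The list reads "duration of sentence, severity of crime, number of incarcerations, ever used VHA services, length of time since last used VHA services", followed by socio-demographic items. Both prior-use variables are therefore named, tied to the linkage outcome and assigned to data sources.

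**Protocol, section 3, Phase 2.** The comparison group was to be matched and released in Massachusetts in the same period. The matching factors were demographics, SUD/MH diagnoses, offense, length of incarceration and number of arrests. Prior VHA use was not among them.

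**SAP.** The comparison group is now historical: all Veterans released in Massachusetts in the two years before PIE began who accessed HCRV services. No matching is mentioned. The baseline comparison covers "baseline demographic characteristics (age, gender, race, ethnicity, marital status, self-rated health"). For the outcome, "we compare our measures of linkages to VA health care following release between PIE participants and our historical comparison group", and "we use bivariate tests (Chi-Square/Fisher Exact Tests and t-tests, as appropriate) to assess the relationship between participation in the PIE intervention" and linkage. The key-variable list adds SUD and MH diagnoses, offense, length of incarceration, arrests, housing, comorbidities and the visit counts. It has no entry for prior VHA use or time since last use. Self-reported baseline utilization is planned for intervention Veterans only.

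**The concern.** Whether someone used VHA before prison, and how recently, is a likely strong predictor of whether they have a VHA contact after release. The protocol treats it as one. The two groups also form in different ways. PIE Veterans told an outreach specialist that they were willing to take part (recruitment text under Phase 1, applied to Phase 2). The historical group is everyone who accessed HCRV. Section 2 of the protocol cites a study of Veterans leaving Los Angeles jails in which, commonly, "Veterans held negative views of the VA and were resistant to link to VHA services upon their release". So it is plausible that willingness to join a VA peer project varies with past VA experience.

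With matching gone and no adjusted analysis planned, the baseline comparison is the main safeguard left, and it omits this factor. The study is not meant to show a significant effect. But Additional Design Considerations says its results will supply effect sizes and sample sizes for the next study, and section 4 says it will help answer whether peer support raises linkage. A bias in the crude difference would carry into both uses.

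**Working it through.** **1. Is the variable anywhere in the SAP?**

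| Item | Protocol, Key Covariates | SAP baseline comparison | SAP key-variable list |
|---|---|---|---|
| Ever used VHA | named | absent | absent |
| Time since last VHA use | named | absent | absent |
| Length of sentence or incarceration | named | absent | present |
| Age, race | named | present | present |

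Two SAP items might seem to fill the gap, but neither does. The visit counts are the outcomes, and no pre-incarceration window is given for them. Self-reported baseline utilization exists in one group only, so it cannot be compared between groups.

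**2. The plan's own figures.** The protocol reports that 43% of eligible HCRV Veterans have no VHA outpatient contact in the first 4 months, so the base linkage rate is 100% − 43% = 57%, as stated. The protocol gives no figure for prior VHA use or for linkage by prior use. Its only effect-size yardstick is an increase of at least 20%, read here as points (57% to 77%). The attached 80% power does not reproduce: 30 against 30 gives 37.5% two-sided. That is a separate matter, and nothing below depends on it.

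**3. Bias from an imbalance, with no PIE effect.** Let s₁ and s₀ be the shares of prior users in the PIE and comparison groups, and g the linkage rate in prior users minus that in never-users. Then

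spurious difference = (s₁ − s₀) × g.

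Assumed inputs: s₁ − s₀ of 10 to 30 points in either direction, and g of 20 to 40 points.

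- Smallest: ±0.10 × 0.20 = ±2 points
- Middle: ±0.20 × 0.30 = ±6 points
- Largest: ±0.30 × 0.40 = ±12 points
- Balanced groups: 0 × g = 0

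**4. A worked case.** Fix comparison linkage at 57%, with s₀ = 50% and g = 30 points. Never-users then link at 57 − 0.5 × 30 = 42% and prior users at 72%.

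- PIE with 80% prior users: 42 + 0.8 × 30 = 66%, a spurious +9 points.
- PIE with 20% prior users: 42 + 0.2 × 30 = 48%, a spurious −9 points, enough to cancel a true gain of 9 points.

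Within each stratum the difference is zero (72% against 72%, 42% against 42%), so a stratified comparison would remove the bias in this example.

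**5. False-positive rate.** Chance of two-sided p < 0.05 with no PIE effect (normal approximation; the comparison size of 200 is an assumption):

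| PIE crude rate | 30 vs 30 | 30 vs 200 |
|---|---|---|
| 57% (balanced) | 5.0% | 5.0% |
| 66% (+9) | 10.9% | 14.5% |
| 69% (+12, with g = 40) | 15.9% | 22.5% |

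**6. Effect on planning the next study.** Two-sided 0.05, 80% power, individual-level, no clustering, and

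n per group = [1.96√(2p̄(1−p̄)) + 0.842√(p₀(1−p₀) + p₁(1−p₁))]² / (p₁ − p₀)².

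Suppose a crude 57% against 77% is observed, which implies n = 86. If 6 of those points are spurious, the real contrast is 57% against 71%, and n = 184. If instead 6 points are hidden, it is 57% against 83%, and n = 48.

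**The case against.** The strongest reply is that the SAP measures what the program calls linkage. The protocol's figure is any VHA outpatient contact after release, with no restriction to Veterans new to VHA. A reader might infer that the SAP would misreport returning patients as newly linked. The documents do not support that: the SAP makes no claim of new linkage, and section 2 describes reentry itself as a break in continuity of care, so a return to care is a wanted outcome. Nor does section 2 tie mistrust of VA to never-users, and no aim asks about never-users separately. This part of the reply stands.

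A reader might also infer that PIE results must be inflated. That does not follow either. Both groups had HCRV contact, which may narrow the difference in prior use, and volunteers could include fewer former VHA patients as well as more.

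It is also fair that the protocol promised a baseline check, not adjustment, and did not match on prior use. A stratified or adjusted difference therefore goes beyond its commitment. It is justified by the SAP's move to an unmatched historical group, and it should be labelled descriptive.

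What the reply does not remove is the omission itself. Two variables that the protocol undertook to compare are missing from the document that governs the analysis, and nothing else in the SAP stands in for them.

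**Conclusion.** The point holds as an inconsistency between protocol and SAP with a conditional consequence. The omission is certain from the text, while its effect on the results is not known. Under the assumed 10 to 30 point imbalance and 20 to 40 point linkage gap, the crude difference would be wrong by 2 to 12 points, upward or downward, and by nothing if the groups are balanced. Against the 20-point yardstick, that is a tenth to three fifths of the effect. Every input to this range is an assumption, because the documents give none of them. The change should be made but does not put the study in question: it is a pilot not designed to show significance, and its main exposure is a biased effect size passed on to the next study.

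**What to change.** 1. Restore two variables to the SAP key-variable list: any VHA use before the index incarceration (yes/no), and time from last VHA use to release. Define both from CDW with the same look-back rule in both groups.
2. Add both to the baseline comparison.
3. Report the linkage difference stratified by, or adjusted for, any prior VHA use beside the crude difference, labelled as a descriptive sensitivity analysis.
4. Optionally, show linkage separately for prior users and never-users. This is not required, since the protocol counts both as linkage.

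The cost is SAP wording and a CDW look-back. CDW is already a named data source, and no new enrollment or contact is needed. The drawback is imprecision: about 30 PIE Veterans split into two strata will give wide intervals, so the stratified or adjusted figure can show whether the crude result is sensitive to prior use but cannot settle it.
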